6.1 Sample Size Considerations

A maximum of 16 participants (SAD and MD cohorts of size 8, randomized 3:1) will be randomly assigned to study intervention such that approximately 16 evaluable participants complete the study.

6.2 Randomization

A randomization schedule will be prepared by the Biostatistics Department of PRA. Eight participants (numbered 101-108) will be assigned to one of the 4 sequences in Part A and 8 participants (numbered 201-208) will be assigned to Part B.

Replacement participants will receive the same randomization number as the participant to be replaced increased by 1000 and will be administered the same treatment (sequence).

7.0 Overview of Planned Analysis

7.1 Changes from Protocol

There are no changes from the protocol.

7.2 Interim Analysis and Key Results

Blinded interim PK reports will be provided by the Biostatistics Department of PRA EDS after completion of each dose level. These reports will be created from blinded concentration data versus scheduled time provided by the PRA bioanalytical laboratory.

7.3 Final Analysis

Draft tables, figures, and listings (TFLs) will be provided after database lock. After Sponsor comments have been incorporated, the TFLs will be finalized and incorporated in the first draft CSR.

8.0 Data Review

8.1 Data Management

Data handling and transfer will take place under the PRA Data Management Plan for the study.

8.2 Acceptance of Data for Summarization

Programming of analysis datasets and TFLs may be ongoing during the data management of the study. However, programming of analysis datasets and TFLs will be completed and quality controlled (QC'd) after database lock. Only quality assured (QA'd) results released by the Safety Laboratory, Bioanalytical Laboratory, or other external data source will be used for the programming of analysis datasets and TFLs for the final report. Any data values requiring investigation or corrections that are identified while programming the analysis datasets and TFLs will be sent to the project Data Manager. If the issue affects the TFLs the Programmer or Statistician who identified the issue will follow it to resolution.

9.0 Definitions and General Analysis Methods

9.1 Analysis Data Presentation

9.1.1 Rounding

In listings, data will be presented with the same precision as the original data. Derived data will be rounded for presentation purposes.

For all safety summaries except PK data summaries, descriptive statistics will be presented with the same precision (same number of decimals or significant figures) as the data they are calculated from. Frequency percentages will be presented as integers.

For all PK data (i.e. concentrations and derived parameters) summaries, descriptive statistics will be presented as integers when values are ≥ 100 or presented with 3 significant digits when values are < 100 . Ratios will be presented with 2 decimals. The T_{max} values and descriptive statistics thereof will be reported with 2 decimals. The coefficient of variation (CV%) will be reported with 1 decimal.

Any p-values will be reported to 4 decimal places; p-value less than 0.0001 will be reported as $p < 0.0001$.

9.1.2 Imputation

Unless otherwise noted, data will not be imputed.

9.1.3 Descriptive Statistics

Unless otherwise indicated, continuous variables will be summarized with the following descriptive statistics: n (number of observations), (arithmetic) mean, standard deviation (SD), minimum value, median, and maximum value.

Categorical data will be summarized with frequencies and percentages. Percentages by categories will be based on the number of participants exposed within a treatment.

For categorical data the categories will be presented in the tables exactly as they appear in the eCRF/Database.

9.1.4 Pooling

Summary statistics will be calculated by study part, treatment (and time point, if applicable). Placebo data will be pooled for Part A (SAD). Placebo data from the periods under fed conditions (i.e. Periods 3 and 4 for Part A) will be reported as a separate treatment for each meal condition.

9.1.5 Unscheduled Measurements

Unscheduled measurements will be included in the listings. With the exception of unscheduled measurements used for baseline, unscheduled measurements will be excluded from the descriptive statistics and statistical analysis.

9.2 Analysis Data Definitions

9.2.1 Baseline Definition

Unless otherwise stated, baseline for post-dose evaluations within each period is defined as the last observation recorded before the first study drug administration in each period. The last observation can be an unscheduled/repeated measurement. If a pre-treatment observation is missing in a given period then the screening value may be used.

In case of triplicate electrocardiogram (ECG) assessments, baseline is defined as the mean of the last recorded triplicate before the first study drug administration in each period. If no triplicate is available before the first study drug administration, the mean of the last recorded duplicate closest to the first study drug administration will be considered as baseline. If no triplicate or duplicate is available, the last single ECG recorded before the first study drug administration will be considered as baseline.

9.2.2 Treatment/Participant Grouping

Label	Grouping
Study Drug	Placebo LY3526318
Study Part / Cohort	Part A: Cohort 1 Part B: Cohort 2
Treatments	Part A (SAD): Placebo (fasted) Placebo (fed, light breakfast) Placebo (fed, high fat) Period 1: 100 mg LY (fasted) Period 2: 250 mg LY (fasted) Period 3: 250 mg LY (fed, light breakfast) Period 4: 250 mg LY (fed, high fat) Part B (MD): Placebo QD 250 mg LY QD

MD = multiple dose; QD = once daily; SAD = single ascending dose.

9.2.3 Common Variable Derivations

Variable	Definition/Calculation	Variable Name*
Change from Baseline	Post-dose observation minus baseline observation	CHG
Analysis Study Day (saf ety data)	Prior to first day of dosing: Date of measurement minus dose date On or after first day of dosing: Date of measurement minus dose date +1	ADY
Scheduled time	Planned time of the assessment. Time in hours of the assessment relative to the planned time of the first drug administration per period.	ATPT/ATPTN
Actual Time	Actual time in hours calculated as the sampling data/time minus the date/time of the first drug administration per period.	ARELTM

*) CDISC ADaM defined variable name

9.2.4 QC

The Analysis Data Model (ADaM) compliant analysis datasets and the TFLs will be QC'd according to the general PRA EDS QC plan.

9.2.4.1 Critical Data

The QC plan requires datasets be classified as critical or non-critical. As the primary objective of this study is to characterize the PK the datasets considered critical are subject level, and PK (ADSL, ADPC, and ADPP). As these are related to the primary objectives these datasets will be double programmed per the QC plan.

9.2.5 ADaM Datasets and Metadata

The analysis datasets will be generated in accordance with Clinical Data Interchange Standard Consortium (CDISC) ADaM Version 2.1.

The following datasets will be generated:

- Subject Level Analysis Dataset(ADSL)
- Adverse Events Analysis Dataset(ADAE)
- Laboratory Analysis Dataset(ADLB)
- Vital Signs Analysis Dataset (ADVS)
- ECG Analysis Dataset(ADEG)
- PK ConcentrationsAnalysis Dataset (ADPC)
- PK Parameter Analysis Dataset(ADPP)

ADaM compliant datasets will be delivered to the Sponsor. A def ine.xml file Version 2 with the corresponding metadata will be included. Analysis results metadata are excluded.

9.3 Software

The statistical analysis and reporting will be done using SAS® for Windows™ Version 9.4 or higher (SAS Institute, Inc.).

PK parameter calculations will primarily be done using Phoenix® WinNonlin® Version 8.1 or higher (Certara, Inc.). Additional PK computations may be performed in SAS®.

9.4 Statistical Methods

9.4.1 Statistical Outlier Determination

No statistical outlier analysis is planned. PK concentrations that appear to be outliers will be assessed on a case-by-case basis.

9.4.2 Predetermined Covariates and Prognostic Factors

There are no predetermined covariates or prognostic factors.

9.4.3 Hypothesis Testing

No formal hypothesis testing will be done.

9.5 TFL Layout

Report layout will be according to the PRA EDS-ICH E3 compliant-Abbreviated CSR Template. The layout of TFLs will be according to the PRA EDS standards. No table shells will be provided. The TFLs will be provided in Adobe PDF format.

Format:

- Page size: LETTER.
- Data in listings will be sorted by study part, subject number, period and time point.
- Data in tables will be sorted by study part, treatment and time point. For assessments with multiple time points the treatment and time point will be presented in a column (one column for treatment and one column for scheduled time), other tables may be presented with one column for each treatment label per part (e.g. AEs and demographic characteristics).
- Column titles will be in title case letters.
- All tables and listings will be in landscape format.
- The treatment labels will be as outlined in Section [9.2.2](#).

10.0 Analysis Sets

Analyses	Entered/Enrolled Set	Safety Set	Pharmacokinetic Set
Disposition Summaries	✓		
Safety Assessments		✓	
Baseline Characteristics		✓	
Primary Analysis			✓
PK Concentrations			✓
PK Parameters			✓

10.1 Enrolled Set

The enrolled set will consist of all participants who sign the informed consent form. This set will be used for disposition summaries.

10.2 Safety Set

The safety set will consist of all participants randomly assigned to study intervention and who take at least 1 dose of study intervention. Participants will be analyzed according to the intervention they actually received. This set will be used for the safety data summaries and baseline characteristic summaries.

10.3 Pharmacokinetic Set

The PK set will consist of all participants who received at least 1 dose of LY3526318 and have at least 1 post baseline evaluable PK sample.

Participants who received a dose of LY3526318 and have evaluable PK parameters will be used for the PK analyses.

11.0 Participant Disposition

The number and percentage of participants randomized, dosed (in each period), and members of each analysis set will be presented. The number and percentage of participants who withdrew from the study prematurely and a breakdown of the corresponding reasons for withdrawal will also be presented. The denominator is the number of subjects randomized.

All disposition data will be listed. All participants who discontinue from the study will be identified.

12.0 Protocol Deviations and Violations

Protocol deviations/violations will be included in the CSR.

13.0 Demographic and Baseline Characteristics

13.1 Demographics

All demographic data as collected during the screenings visit will be listed by participant.

Participant demographics will be summarized descriptively for all participants by study part. The summary will include the participants' age (in years), gender, race, ethnicity, weight (in kg), height (in cm), and body mass index (BMI) (in kg/m²). Subjects' age will also be presented in categories (18-64 years and >=65 years). Demographics will be summarized for the safety and PK sets.

13.2 Medical History

Medical history will be listed.

13.3 Other Baseline Characteristics

The results of drug and alcohol screen at screening and admission will be listed.

Serology (Hepatitis B surface antigen, Hepatitis C antibody and HIV) at screening will be listed.

The results of pregnancy tests at screening, admission and at the end of the study will be listed.

All SARS-CoV-2 test results will be listed.

14.0 Concomitant Medications

Concomitant medication will be listed by participant. Medications with an end date prior to the first dose of study drug will be considered prior medications and will be identified as such in the listing. If a partial date allows a medication to be considered concomitant it will be categorized as such.

Concomitant medications will be coded according to the World Health Organization–Drug Dictionary Enhanced (WHO-DDE) (version as per the Dictionary Coding Conventions).

15.0 Treatment Compliance and Exposure

All exposure data will be listed by participant.

16.0 Pharmacokinetic Analyses

16.1 Pharmacokinetic Variables

16.1.1 Plasma Variables

16.1.1.1 Concentrations

- Plasma concentration of LY3526318
- Plasma concentration of LSN3528305

16.1.1.2 Parameters

- Plasma PK parameters for LY3526318 as defined in [Table 2](#)
- Plasma PK parameters for LSN3528305 as defined in [Table 2](#)

Table 2: Plasma PK Parameters

Parameter	Description	SAD	MD Day 1	MD Day 5	SAS Programming Notes
C_{max}	Maximum plasma concentration. Observed peak analyte concentration obtained directly from the experimental data without interpolation, expressed in concentration units.	✓	✓	✓	Cmax from WNL
T_{max}	Time to maximum plasma concentration. First observed time to reach peak analyte concentration obtained directly from the experimental data without interpolation, expressed in hours(h).	✓	✓	✓	Tmax from WNL
AUC_{0-t}	Area under the concentration-time curve (time 0 to time of last quantifiable concentration).	✓			AUClast from WNL
AUC_{0-inf}	Area under the plasma concentration-time curve (time 0 to infinity). Percent extrapolation less than or equal to 20% is required to obtain a reliable AUC_{0-inf} .	✓			AUCINF_obs from WNL If $AUC_ \%Extrap_obs > 20\%$ then parameter is flagged
AUC_{0-24}	Area under the plasma concentration-time curve from time 0 to 24 hours post-dose.	✓			AUC_{0-24} from WNL where partial time =24h, if missing for a participant then AUC at nominal time 24h from summary file is used for AUC_{0-24}
AUC_{0-tau}	Area under the plasma concentration-time curve over the dosing interval (time 0 to 24h) at steady state.		✓	✓	AUC_{tau} from WNL where tau is equal to 24h, if missing for a participant then AUC at nominal time 24h from summary file is used for AUC_{0-tau}
λ_z	Terminal phase rate constant calculated by linear regression of the terminal log-linear portion of the concentration vs. time curve. Linear regression of at least 3 points and an adjusted r^2 greater than 0.80 are required to obtain a reliable λ_z .	✓		✓	Lambda_z from WNL If Rsq adjusted $\leq .80$ then parameter is flagged
$t_{1/2}$	Terminal phase half-life expressed in hour (h). Percent extrapolation less than or equal to 20% and adjusted r^2 greater than 0.80 is required to obtain a reliable $t_{1/2}$.	✓		✓	HL_Lambda_z from WNL If $AUC_ \%Extrap_obs > 20\%$ or Rsq adjusted ≤ 0.80 then parameter is flagged

Parameter	Description	SAD	MD Day 1	MD Day 5	SAS Programming Notes
CL/F	Apparent oral clearance, calculated as Dose/AUC _{0-inf} for SAD regimens or Dose/AUC _{0-tau} for the MAD regimen on Day 5; LY3526318 only	✓		✓	CL_F_obs or CLss_F from WNL respectively. If AUC_%Extrap_obs > 20% or Rsq adjusted ≤ 0.80 then parameter is flagged
V _z /F	Apparent volume of distribution calculated as (CL/F)/λ _z ; LY3526318 only	✓			Vz_F_obs from WNL If AUC_%Extrap_obs > 20% or Rsq adjusted ≤ 0.80 then parameter is flagged
V _{ss} /F	Apparent volume of distribution at steady state, calculated as CL/F*MRT			✓	Vss_F_obs from WNL
AR _{AUC}	Accumulation ratio AUC _{0-tau}			✓	AUC _{0-tau} (Day 5)/AUC _{0-tau} (Day 1), calculated in SAS

Note: AUCs will be calculated using linear up/log down, expressed in units of concentration x time.

MD = multiple dose; SAD = single ascending dose; WNL = WinNonlin.

*) In end-of-text TFLs, subscript will not be used.

All of the flagged parameters will be listed and will be included in the descriptive summaries and all statistical comparisons.

16.2 Pharmacokinetic Summaries

16.2.1 Pharmacokinetic Concentrations

Plasma concentrations for LY3526318 and LSN3528305 below the quantifiable limit (BQL) will be set to ½ lower limit of quantification (LLOQ) in the computation of mean concentration values. Descriptive statistics (number of participants, arithmetic mean, SD, CV%, median, minimum, maximum, geometric mean and geometric CV%) will be used to summarize the plasma concentrations by treatment at each scheduled time point. If over ½ of the participants in a given cell have values BQL then the descriptive statistics will not be presented and will instead display as BQL for the mean and minimum. With the exception of maximum, all other statistics will be missing.

Linear and semi-logarithmic plots of the geometric mean plasma concentration by scheduled sampling time will be presented by study part and treatment for each analyte separately. These plots will show time in hours. The plots will match the summary table results and will not have an observation at a given time point if more than half of the participants have values BQL.

The SAD treatments will be presented in one plot. Separate plots will be provided for food effect results. The full profile of the MD treatment will be presented in one plot from Day 1 to the last scheduled time point). In addition, an overlay plot for the MD treatment will be presented, showing Day 1 and Day 5 in one plot.

Linear and semi-logarithmic plots of the combined individual plasma concentrations by actual sampling times will be provided by treatment for each analyte (one treatment per page). For the MD Part, the full profiles will be presented. These plots will show time in hours and will use the BQL handling procedure described below for "Pharmacokinetic Parameters".

Linear and semi-logarithmic plots of the individual plasma concentrations by actual sampling times will be provided by analyte and participant (one participant per plot, 6 plots per page). All treatments will be displayed on the same plot. These plots will show time in hours. MD plots will show the complete profile. Individual plots will use the BLQ handling procedure described below for "Pharmacokinetic Parameters". The Y axis will be allowed to adjust dynamically for each individual plot.

All individual participant plasma concentration data will be listed and included in the summary tables.

16.2.2 Pharmacokinetic Parameters

Plasma PK parameters for LY3526318 and LSN3528305 will be estimated using non-compartmental methods with WinNonlin®.

The plasma PK parameters will be estimated from the individual concentration-time profiles. In estimating the PK parameters, BQL values at the beginning of the profile will be set to zero. BQL values that occur after the first quantifiable point will be considered missing. Values that are embedded between BQLs, or quantifiable values occurring after 2 or more BQLs, will be set to missing at the discretion of the pharmacokineticist. Actual sampling times will be used in all computations involving sampling times. If the actual time or dose time is missing, the scheduled time may be substituted in order to calculate the PK parameter.

Descriptive statistics (number of participants, arithmetic mean, SD, CV%, median, minimum, and maximum, geometric mean and geometric CV%) will be used to summarize the calculated plasma PK parameters by treatment. For T_{max} , only median, minimum and maximum will be presented.

The points to be included in the λ_z range will be determined by the pharmacokineticist after inspection of the semi-log concentration-time profiles and the points will be indicated in the plots. At least 3 points will be required to be used. The C_{max} data point will not be included. Parameters based on r^2 adjusted below 0.80 or %AUC_{extra} above 20% will be flagged but not excluded from descriptive statistics or any statistical analysis.

16.2.2.1 Dose-Proportionality

Dose proportionality may be explored for C_{max} , AUC_{0-t} , and AUC_{0-inf} (for SAD) using the power model as described by Smith et al, 2000. In the power model, the \log_e -transformed parameters (Y) are assumed to be linearly related to the \log_e -transformed Dose:

$$\log_e = \beta_0 + \beta_1 * \log_e(\text{Dose})$$

Results will be presented in a table. The table will show the results of the dose proportionality assessment as shown in Table 2 in Smith et al, 2000. If the 90% confidence Intervals (CIs) for the dose-normalized ratio of PK geometric mean values (over the full range of doses tested) is included in the interval (0.8, 1.25) dose proportionality can be assumed. The maximum fold dose range in which dose proportionality can be concluded will also be reported.

16.2.2.2 Food Effect

For the dose level administered in a fasted and fed state (Part A), an analysis of variance (ANOVA) will be performed on AUC_{0-t} , AUC_{0-inf} and C_{max} using the SAS procedure for mixed effect models (PROC MIXED). The PK parameters will be natural logarithm transformed prior to the analysis. The ANOVA model will include fixed effects for treatment and a random effect for participant. From this model the back-transformed least-squares means (LSMeans) for each treatment and their ratio will be presented. The ratio of least-squares geometric means between the test treatment (fed) to the reference (fasted) and the corresponding 90% CI will be presented.

For T_{max} , a Wilcoxon signed rank test will be performed. The median T_{max} for each treatment and the median of pairwise differences between the treatments (fed-fasted) will be presented along with the 90% CIs, and p-values.

17.0 Safety Analyses

17.1 Safety Variables

The following safety variables will be listed and/or summarized:

- Adverse Events (AEs)
- Vital Signs
 - Supine Blood Pressure
 - Systolic Blood Pressure
 - Diastolic Blood Pressure
 - Heart rate
 - Oral body temperature
 - Body Weight
- ECG
 - Heart Rate
 - PR Interval
 - QRS-Duration
 - QT Interval
 - QTc (Fridericia) Interval
- Clinical Laboratory Evaluations
 - Clinical Chemistry
 - Hematology
 - Urinalysis
- Physical Examinations
- Columbia-Suicide Severity Rating Scale (C-SSRS)

17.1.1 Adverse Events

All AE summaries will include only treatment-emergent AEs. Treatment-emergent AEs (TEAE) are those which occur after the first dose of study drug. For the SAD part, TEAEs occurring following dosing in a specific period but before dosing in the next period will be attributed to that specific period.

A breakdown of the number of events, and the number and percentage of participants reporting each TEAE, categorized by system organ class (SOC) and preferred term (PT) coded according to the Medical Dictionary for Regulatory Activities (MedDRA) (version as per the Dictionary Coding Conventions), will be presented by treatment, overall active and overall for each study part, in descending order of total number of events by SOC and PT. One table is presented for all TEAEs and one table is presented for TEAEs considered to be related to the study medication. Participants will only be counted once within each SOC or PT per treatment.

Additionally, a summary table with TEAEs by severity and relationship to study drug will be presented by study part and treatment.

TEAEs of which the relationship to study drug will be classified as 'possibly', 'likely', or 'definitely' will be regarded as related, while TEAEs that are classified as 'none', or 'unlikely' will be regarded as not related in the tables

A listing of AEs leading to study discontinuation will be provided.

All AEs (including non-treatment-emergent events) recorded on the eCRF will be listed.

The following missing data will be imputed as defined (for calculations only/will not be presented):

- Missing AE start and/or end times for the calculation of onset and duration will be assumed to be at 00:01 for a start time and 23:59 for end times
- Missing AE severity or relationship will be assumed to be severe or related, respectively
- Missing AE start times for the determination of treatment emergence will be assumed to occur after treatment unless partial date documents the AE as happening prior to treatment
- Missing AE start times for the determination of treatment assignment will be assumed to occur after treatment on the recorded date one minute after dosing
- Missing AE start date will be assumed to be after treatment for the determination of TEAE and on treatment for single treatment studies but will not be attributed to treatment in studies with multiple treatments

For the US Clinical Trials Registry (CTR), a CTRAE summary table and the CTRAESUMM SAS dataset will be provided separately from the TFL created for CSR. The table and corresponding dataset will be created according to the specifications provided by the Sponsor.

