8.3.1. Time Period and Frequency for Collecting AE and SAE Information

All SAEs will be actively collected from the signing of the ICF until the follow-up visit at the time points specified in the SoA (Section 1.3) and until 30 days after the last dose for spontaneously reported SAEs.

All AEs will be collected from the signing of the ICF until the follow-up visit OR participation in the study has ended.

Adverse events that begin before the start of study intervention but after signing of the ICF will be recorded on the AE CRF.

Although all AEs after signing the ICF are recorded by the site in the CRF/electronic data entry, SAE reporting to the sponsor begins after the participant has signed the ICF and has received study intervention. However, if an SAE occurs after signing the ICF, but prior to receiving study intervention, it needs to be reported ONLY if it is considered reasonably possibly related to study procedures.

All SAEs will be recorded and reported to the sponsor or designee immediately, and under no circumstance should this exceed 24 hours, as indicated in Appendix 3 (Section 10.3). The investigator will submit any updated SAE data to the sponsor within 24 hours of it being available.

Investigators are not obligated to actively seek AEs or SAEs after conclusion of the study participation. However, if the investigator learns of any SAE, including a death, at any time after a participant has been discharged from the study and he/she considers the event to be reasonably

related to the study intervention or study participation, the investigator must promptly notify the sponsor.

Pregnancy (maternal or paternal exposure to the study intervention) does not meet the definition of an AE. However, to fulfill regulatory requirements, any pregnancy should be reported following the SAE process to collect data on the outcome for both mother and fetus.

The designated medical monitor of the sponsor will monitor safety data throughout the course of the study. The sponsor and/or its designee will review SAEs within appropriate timeframes to meet reporting obligations imposed by regulatory authorities. All SAEs and unexpected AEs for this study will be reported to regulatory authorities in accordance with local laws, directives, and regulations (Section 8.3.4).

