- Alternative causes, such as underlying disease(s), concomitant therapy, and other risk factors, as well as the temporal relationship of the event to study intervention administration will be considered and investigated.
- The investigator will also consult the IB and/or Product Information, for marketed products, in his/her assessment.
- For each AE/SAE, the investigator **must** document in the medical notes that he/she has reviewed the AE/SAE and has provided an assessment of causality.
- There may be situations in which an SAE has occurred, and the investigator has minimal information to include in the initial report to the sponsor or designee. However, it is very important that the investigator always make an assessment of causality for every event before the initial transmission of the SAE data to the sponsor or designee.
- The investigator may change his/her opinion of causality in light of follow-up information and send an SAE follow-up report with the updated causality assessment.
- The causality assessment is one of the criteria used when determining regulatory reporting requirements.

Follow-up of AEs and SAEs

- The investigator is obligated to perform or arrange for the conduct of supplemental measurements and/or evaluations as medically indicated or as requested by the sponsor or designee to elucidate the nature and/or causality of the AE or SAE as fully as possible. This may include additional laboratory tests or investigations, histopathological examinations, or consultation with other health care professionals.
- If a participant dies during participation in the study or during a recognized follow-up period, the investigator will provide the sponsor or designee with a copy of any post-mortem findings including histopathology.
- New or updated information will be recorded in the originally completed CRF.
- The investigator will submit any updated SAE data to the sponsor or designee within 24 hours of receipt of the information.

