ICH	International Council for Harmonisation
IEC	Independent Ethics Committee
Informed consent	A process by which a participant voluntarily confirms his or her willingness to participate in a particular study, after having been informed of all aspects of the study that are relevant to the participant's decision to participate. Informed consent is documented by means of a written, signed and dated informed consent form.
investigational product	A pharmaceutical form of an active ingredient or placebo being tested or used as a reference in a clinical trial, including products already on the market when used or assembled (formulated or packaged) in a way different from the authorized form, or marketed products used for an unauthorized indication, or marketed products used to gain further information about the authorized form.
IRB	Institutional Review Boards

Term	Definition
Lilly	Eli Lilly and Company
MD	multiple dose
NOAEL	no-observed-adverse-effect level
participant	Equivalent to CDISC term “subject”: an individual who participates in a clinical trial, either as recipient of an investigational medicinal product or as a control
PK	pharmacokinetic(s)
QTcF	Fridericia's corrected QT interval
SAD	single-ascending dose
SAE	serious adverse event
SARS-CoV-2	severe acute respiratory syndrome coronavirus 2
screen	The act of determining if an individual meets minimum requirements to become part of a pool of potential candidates for participation in a clinical study.
SoA	Schedule of Activities
SOP	standard operating procedure
TBL	total bilirubin
TEAE	Treatment-emergent adverse event: An untoward medical occurrence that emerges during a defined treatment period, having been absent pretreatment, or worsens relative to the pretreatment state, and does not necessarily have to have a causal relationship with this treatment.
t_{max}	time to C _{max}
TRPA1	transient receptor protein ankyrin-1
t_{1/2}	elimination half-life
V_{ss/F}	apparent volume of distribution at steady state
V_{z/F}	apparent volume of distribution
WOCBP	women of childbearing potential

11. References

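### SAP 17.1.1 leaves out the protocol's worsening clause from the TEAE definition without declaring it, so a pre-dose AE that worsens after dosing may be missing from the AE summaries

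*SAP*

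**What the plan says.** Protocol Appendix 7 (10.7) defines a TEAE as "An untoward medical occurrence that emerges during a defined treatment period, having been absent pretreatment, or worsens relative to the pretreatment state". SAP 17.1.1 is shorter: "Treatment-emergent AEs (TEAE) are those which occur after the first dose of study drug". The same SAP section limits the tables: "All AE summaries will include only treatment-emergent AEs".

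The SAP's imputation rules show how the before-or-after question is decided: "Missing AE start times for the determination of treatment emergence will be assumed to occur after treatment", unless a partial date shows otherwise. A parallel rule covers missing start dates. Nothing in the SAP uses a change in severity to make an earlier event treatment-emergent.

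SAP 7.1 states "There are no changes from the protocol". SAP 3.0 gives the SAP precedence over the protocol's statistical text and undertakes to point out substantial differences.

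On data collection, Protocol 8.3.1 says "Adverse events that begin before the start of study intervention but after signing of the ICF will be recorded on the AE CRF". On follow-up of an existing event, Protocol 10.3.3 says "New or updated information will be recorded in the originally completed CRF".

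**The concern.** AEs and SAEs are the secondary safety endpoints in both parts. Screening can run for up to 28 days, and AEs are collected at screening and on Day -1, so some events may already be open at the first dose. A mild symptom present at admission that becomes moderate a few hours after dosing is the case the protocol's worsening clause covers. A programmer working from SAP 17.1.1 would test only whether the AE started after the first dose, and nothing in the SAP would show that this is narrower than the protocol. The incidence and severity tables could then omit an event that the protocol calls treatment-emergent.

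**Working it through.** There is no stated figure to reproduce. The check compares the two definitions and then sizes the effect of one participant.

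**Step 1. Apply both rules to the possible cases**, reading the SAP's rule through its start-time logic.

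| Case | Protocol | SAP 17.1.1 |
|---|---|---|
| Absent before dosing, starts after | TEAE | TEAE |
| Starts before dosing, unchanged after | Not | Not |
| Starts before, worsens after, entered as a new post-dose AE | TEAE | TEAE |
| Starts before, worsens after, kept on one record | TEAE | Not |
| Intermittent, present before, recurs after and no worse, entered as a new AE | Not | TEAE |

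The rules part in the last two rows. The fourth row is the loss. The fifth runs the other way, because the SAP also omits the requirement that the event was absent before treatment.

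**Step 2. Which record would hold the worsening?** Protocol 10.3.3 sends updates to the existing CRF, which suggests the fourth row, but it does not mention severity changes or onset dates. Protocol 10.3.1 treats an aggravated condition as an AE, which permits the third row. Neither document says that a rise in severity opens a new record. The outcome therefore depends on eCRF conventions that are not shown.

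**Step 3. Size of one participant.** SAP 9.1.3 bases percentages on participants exposed within a treatment. Part A has 4 sequences of 2, with one sequence on placebo in each period, so each period has 6 on active drug and 2 on placebo. SAP 9.1.4 and 9.2.2 pool fasted placebo and keep each fed meal condition separate. Part B has 6 active and 2 placebo.

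- Any active column, Part A or B: 1/6 = 16.7 points.
- Fasted placebo, Periods 1 and 2: 2 + 2 = 4 planned, 1/4 = 25 points.
- Either fed-placebo column, or Part B placebo: 1/2 = 50 points.

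The documents give no expected number of such events, so these are sizes per participant and not a forecast.

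**Step 4. Part A across periods.** SAP 17.1.1 assigns a TEAE to the period in which it occurs. An event that starts on placebo in Period 1 (sequence 1) and worsens after active drug in Period 2 is already a TEAE. If kept on one record, it stays under placebo. The SAP resets baseline each period for other measurements (9.2.1) but has no equivalent for AEs.

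**The case against.** The strongest answer is that the loss is inferred. The SAP's word is occur, not start, and under Protocol 10.3.1 a post-dose exacerbation can itself be an AE that occurs after dosing. The follow-up sentence in Protocol 10.3.3 sits in general text about working up events and does not require one record per event. This stands in part: it makes the effect conditional. It does not remove the difference, because the SAP's own rules decide emergence by start time or date and no text requires a new record.

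A reader might infer that worsened events leave the report, or that the rule can only undercount. Neither follows. SAP 17.1.1 lists all AEs, including non-treatment-emergent ones, and separate listings cover SAEs and AEs leading to discontinuation. With 16 planned participants those listings can be read person by person. The fifth row of the table and the defaults for missing start times show that the rule can also overcount. A reader might likewise apply the 50-point figure to all placebo data, but pooled fasted placebo has 4 planned participants.

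It is also fair to say that the cross-period case is uncommon. Doses are at least 1 week apart, the earlier formulation's half-life was 9.72 to 13.5 hours, and earlier TEAEs were mild. The protocol sets no rule for attributing a worsening to a period. Finally, the protocol's definition sits in an abbreviations appendix and its safety-analysis section does not use the term, so the omission may be an oversight. It is still the only TEAE definition the protocol gives.

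**Conclusion.** The point holds in conditional form. The SAP's TEAE definition is narrower than the protocol's on worsening, and SAP 7.1 does not declare it. A pre-dose AE that worsens after dosing is missing from the TEAE summaries if it stays on one CRF record, and is counted if the worsening is entered as a new AE. It remains in the listings either way.

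Few events are likely. Each would move a column by about 17, 25 or 50 percentage points, depending on the column. This assumes that planned numbers are met and that emergence is programmed from the AE start. The registry AE table follows sponsor specifications that are not shown, so nothing is concluded about it. With no formal testing planned, the consequence is a misclassified safety summary, not a wrong inference.

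**What to change.** Replace the definition in SAP 17.1.1 with the protocol's. A TEAE is an AE that was absent before treatment and first occurs after the first dose, or one already present that worsens in severity after that dose. Add that a post-dose worsening is identified either from a new AE record with a post-dose start or from a dated severity change.

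For Part A, preferably add that a worsening is attributed to the period in which it occurs. This is a sensible extension, not something the protocol requires.

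If the sponsor prefers the narrower rule, SAP 7.1 should declare it and give the reason.

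The cost is two or three SAP sentences and one derivation flag. The flag works only if the eCRF dates severity changes or sites enter a worsening as a new record. The documents do not show which applies, so the finalised eCRFs named in SAP 3.0 should be checked, and a short completion instruction issued if neither is in place.
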